7.4.2. Time to Clinical Worsening (TTCW)

A clinical worsening event is defined using two definitions (a composite endpoint):

Protocol Definition

1. Death from any cause
2. Hospitalization for worsening PAH (any hospitalization for worsening PAH, lung or heart and lung transplantation, atrial septostomy, or initiation of parenteral prostanoid)
3. Disease progression, defined as a decrease of more than 15% from baseline in the 6MWD combined with WHO FC III or IV symptoms at 2 consecutive visits separated by at least 14 days. The time of disease progression is at the time of initial visit.

Additional Definition

1. Death from any cause
2. Hospitalization for worsening PAH (any hospitalization for worsening PAH, lung or heart and lung transplantation, atrial septostomy, or initiation of parenteral prostanoid therapy)

3. Disease progression defined as a decrease of more than 15% from Baseline in the 6-minute walk distance (6MWD) (2 consecutive visits separated by at least 14 days), combined with World Health Organization (WHO) Functional Class (FC) III or IV symptoms at 2 consecutive visits separated by at least 14 days. Also requires the absence of a clinical rationale (e.g., an intercurrent event that would be expected to worsen the walk and functional class independent of pulmonary hypertension progression).
4. Addition of parenteral prostanoid therapy or increase of greater than 10% of any prostanoid
5. Appearance of worsening signs and symptoms of right heart failure

TTCW will be adjudicated separately for each definition of clinical worsening. TTCW is defined as the first occurrence of any of the above events (separately for each definition).

The CEAC adjudicated CWEs include the date and reason will be incorporated into the clinical database. Adjudicated TTCW is defined as the number of days from randomization date to the date of the first adjudicated CWE. Subjects who do not have an adjudicated CWE during the 24 weeks of the main study will be censored at the first OLE dose date if enrolled into OLE or if not enrolled into OLE, the minimum of last dose of study drug + 30 days or date of last contact in the main study.

Sensitivity analysis for TTCW will be performed based on investigator assessed CWE. Investigator assessed TTCW is defined as the number of days from randomization date to the first investigator assessed CWE. Subjects who do not have an investigator assessed CWE during the 24 weeks of the main study will be censored at the date of last contact in the main study.

For a subject with CWE (adjudicated or investigator assessed) due to disease progression and the initial assessment was on-treatment during the main study, and the confirmation assessment was off treatment or post Week 24, the subject will be counted as on-treatment CWE for the main study. The date of CW is the date of the initial assessment.

The time from randomization to the adjudicated clinical worsening event will be summarized using Kaplan-Meier estimates and compared between each active treatment and placebo treatment group using the stratified log-rank test stratified by the randomization strata. Kaplan-Meier (KM) estimates of the survival distributions of the time-to-event will be tabulated and graphed by treatment group. The tabulation will include the KM estimate of the medians, 25th and 75th quartiles, and corresponding 95% CIs, if they can be estimated. The tabular and graphical summaries will include the at-risk counts for every visit. The number and percent of subjects censored, reason for censoring, and with events will be presented overall and for each visit, using last day of the visit window by treatment group. The hazard ratio and 95% CI a will be determined based on the semi-parametric Cox regression model stratified by randomization strata to estimate the magnitude of the effect. In order to test assess the effects of the stratification factors, the unadjusted/not stratified hazard ratio with associated 95% CI will be presented. KM plots will also be presented for each stratification factor by treatment group.

Sensitivity analysis on TTCW will be performed based on investigator reported clinical worsening.

The CEACP adjudicated and investigator reported CWE data will be listed.

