Study Week¹ (Days)	-4 Wks² (D-28 to D-1) Clinic	D1 Clinic	Wk 2 (D14) Telemed/ Phone Call	Wk 4 (D28) Clinic	Wk 8 (D56) Clinic or Home	Wk 12 (D84) Clinic	Wk 18 (D126) Clinic or Home	Wk 24 (D168) Clinic	Wk 28 (D196) FU ^{3/} ET ^{3,4} Clinic or Home
Vital Signs (BP, HR, RR, temp, oxygen saturation)	X	X		×	×	×	X	X	X
12-Lead ECG ¹²	X	X		×	×	×	×	X	×
Laboratory – Hematology, Coagulation ¹³ , Chemistry, urinalysis,	X	X		×	×	×	×	X	×
Columbia-Suicide Severity Rating Scale (C-SSRS)	X	X		×		×	×	X	X
Hospital Anxiety and Depression Scale (HADS)	X	X		×		×	×	X	X
Quick Inventory of Depressive Symptoms (QIDS-C)	X	X		×		×	×	X	X
Efficacy-Related Assessments									
5 TWM5	X	X		X		X		X	
Right Heart Catheterization (RHC) ¹⁴	X							X	X^{14}
Echocardiography ¹⁵	X					X		X	
WHO FC	X	X		X		X		X	
Plasma NT-proBNP level		×		×		×		×	
PAH Symptoms and Impact Questionnaire (PAH-SYMPACT)		X				×		X	
Actigraphy ¹⁶					\	$X \rightarrow$			
Pharmacokinetics									
Rodatristat PK Sampling ¹⁷		X		X		X		X	
Selexipag PK sampling ¹⁸		X		×					
Pharmacodynamics		Α		Þ		Þ		Α	
Ullile J-HIAA		< >		< >		< >		< >	
Plasma 5-HIAA ¹⁷		X		×		×		X	
Other									
Optional Blood for Future Research Sample		X						X	
Pharmacogenetic Samples		X						X	

Clinical Study Protocol Altavant Sciences GmbH

Visits at Week 2 (Telemed/Phone Call) and Week 4 (clinic visit) can occur within +/-2 days from the randomization date; Visits at Weeks 8 (Telemed/Phone call), 12 (clinic), 18 (clinic or home visit), 24 and 28/Follow Up (clinic) can occur within +/-5 days from the randomization date.

² Screening may be broken up into more than 1 visit, if necessary. Once all screening procedures are complete and the Investigator determines that the patient is eligible, the site must upload/send the required supporting documentation for approval by the Sponsor.

withdraw consent will continue to be followed for vital status from public records such as government vital statistics or obituaries, as allowed by local law, or periodic contact Patients who early terminate from the IP should be asked to return for visits as scheduled for ongoing assessments through the Week 28 Visit. Patients who withdraw consent should be asked to complete the Week 28 Visit for safety. Patients who have not completed the study as planned (through Week 24) cannot participate in OLE. Patients who (about every 6 to 12months).

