8.2.1. Investigational Product Discontinuation

If a patient is permanently discontinued from the IP, but agrees to study visits, the patient will come in for the Early Termination Visit and continue attending clinic visits as scheduled through the 24-week visit (from first dose). A final follow-up visit will not be required.

If a patient prematurely discontinues IP prior to the Week 24 Visit, the Investigator will make every attempt to perform a RHC, as clinically feasible, prior to or within 7 days of IP discontinuation (but after at least 12 weeks of IP), and prior to initiation of any new PAH medications.

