8.3. Lost to Follow up

A patient will be considered lost to follow up if he or she repeatedly fails to return for scheduled visits and is unable to be contacted by the study site.

The following actions must be taken if a patient fails to return to the clinic for a required study visit:

- The site must attempt to contact the patient and reschedule the missed visit as soon as possible and counsel the patient on the importance of maintaining the assigned visit schedule and ascertain whether or not the patient wishes to and/or should continue in the study.
- Before a patient is deemed lost to follow up, the Investigator or designee must make every effort to regain contact with the patient (where possible, 3 telephone calls and, if necessary, a certified letter to the patient's last known mailing address or local equivalent methods). These contact attempts should be documented in the patient's medical record.
- Should the patient continue to be unreachable, he/she will be considered to have withdrawn from the study.
- Patients who withdraw consent will continue to be followed for vital status from public records such as government vital statistics or obituaries, as allowed by local law, or periodic contact (about every 6 to 12 months).

Discontinuation of specific sites or of the study as a whole are handled as part of Appendix 5.

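### Adjudicated TTCW counts events up to Week 24 but stops event-free follow-up at last dose + 30 days, so censoring depends on the outcome and Kaplan-Meier and hazard estimates are modestly biased upward

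*SAP*

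**What the plan says.** **Event rule.** SAP 7.4.2: "Adjudicated TTCW is defined as the number of days from randomization date to the date of the first adjudicated CWE". No limit relative to last dose is stated. The window is the 24 weeks: "Subjects who do not have an adjudicated CWE during the 24 weeks of the main study will be censored".

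**Censoring rule.** Event-free subjects are censored at first OLE dose if they enter the OLE. Otherwise they are censored at "the minimum of last dose of study drug + 30 days or date of last contact in the main study".

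**Who falls under the second branch.** The footnotes to the main-study Schedule of Assessments (Protocol 1.3) state: "Patients who have not completed the study as planned (through Week 24) cannot participate in OLE".

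**Follow-up after stopping drug.** The same footnotes say: "Patients who early terminate from the IP should be asked to return for visits as scheduled for ongoing assessments through the Week 28 Visit". Protocol 8.2.1 keeps those who agree to visits in follow-up to the 24-week visit. Protocol 8.3 adds: "Patients who withdraw consent will continue to be followed for vital status from public records". Events after last dose + 30 days can therefore be observed.

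**Sensitivity analysis.** Subjects without an investigator-assessed event "will be censored at the date of last contact in the main study". No last-dose limit applies there.

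**Use.** SAP 7.4.2 plans KM curves, a stratified log-rank test and a stratified Cox hazard ratio for each active arm against placebo.

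**The concern.** The event window and the follow-up window differ. Take a patient who stops drug on Day 28 and attends visits to Week 24. With an adjudicated event on Day 140, that patient is at risk throughout and is an event on Day 140. Without an event, the same patient leaves the risk set on Day 58. Whether Days 59 to 140 count depends on what happens later, so the censoring is informative by construction.

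Removing only patients already known to be event-free shrinks the denominators and leaves the events in place. KM risk and hazard estimates rise, by more where stopping is more frequent or earlier. If stopping differs between arms, the hazard ratio moves away from 1 with no treatment effect.

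The investigator-assessed analysis does not have this mismatch, but it also changes the assessor. If the two analyses disagree, a reader cannot tell adjudication from censoring.

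**Working it through.** The documents state no TTCW event rate, event count, hazard ratio or discontinuation rate, so there is no planned figure to reproduce. All rates below are assumptions.

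**Hand example.** 30 patients; 9 stop on Day 28 and stay in follow-up; events on Days 100, 120 and 140, the last in a stopper.

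- SAP rule: the 8 event-free stoppers are censored on Day 58, leaving 22 at risk on Day 100. KM risk = 1 − (21/22)(20/21)(19/20) = 3/22 = 13.6%.
- Everyone followed to Week 24: 3/30 = 10.0%.
- Events and follow-up both stopped at last dose + 30 days: 2/21 = 9.5%.

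**General form.** Assume constant hazard λ, equal on and off drug, and all stoppers followed to Day 168. A share p stops, with last dose uniform on Days 7 to 161.

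- True 24-week risk 12%: λ = −ln(0.88)/168 = 0.00076 per day; S(t) = exp(−λt).
- Share of patients who are stoppers past last dose + 30 days by day t: q(t) = p × (t − 37)/154, held between 0 and p.
- At risk under the SAP rule: S(t) − q(t)·S(168). The subtracted term is the stoppers who will be event-free at Day 168.
- Hazard that KM and Cox see: λ·S(t) / [S(t) − q(t)·S(168)], which is at least λ.
- KM risk = 1 − exp(−integral of that hazard from 0 to 168).

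| Stopping | KM risk, SAP rule | Ratio to KM at 5% stopping |
|---|---|---|
| 0% | 12.0% | – |
| 5% | 12.2% | 1.00 |
| 10% | 12.4% | 1.02 |
| 15% | 12.6% | 1.03 |
| 25% | 13.0% | 1.07 |
| 35% | 13.6% | 1.11 |

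Simulation of the same setting gives 13.5% at 35%. Events per person-time are overstated by 1.6%, 8.4% and 12.2% at 5%, 25% and 35% stopping. The spurious rate ratios against 5% are 1.084/1.016 = 1.07 and 1.122/1.016 = 1.10.

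**Retention.** If half the stoppers leave 28 days after last dose, KM is 12.5% at 25% stopping and 12.8% at 35%. If all leave and no later event is counted, it is 12.0%.

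**Null hazard ratio.** Simulation, true risk 10% in both arms, 30% against 10% stopping, full retention:

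- Stops spread over 168 days: KM 11.1% against 10.3%, HR 1.08.
- All stops by Day 84: HR 1.14. All by Day 28: HR 1.18.
- Crude percentage with an event: 10.0% in both arms throughout.
- Either consistent rule (all events to Week 24, or everything stopped at last dose + 30 days): HR 1.00.

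**Test size.** With 30 per arm and 30% or 40% against 10% stopping, the two-sided log-rank test rejects in 4.6% to 5.3% of null runs. The tails are uneven: 3.0% to 3.8% against the arm with more stopping, 1.5% to 1.9% the other way.

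**The case against.** **Intent.** SAP 7.4.2 has a rule labelling some progression events as on-treatment, and SAP 7.4.6 defines on-treatment as ending at last dose + 30 days, the same limit. One can argue that an on-treatment analysis was meant and its event window left unwritten, or set in the adjudication charter, which is not among the documents. Under that reading there is no bias. But the first rule only classifies progression confirmed later, the second belongs to TTCI, and neither excludes a later event from TTCW. A programmer following the text would count it.

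**Retention.** Follow-up to Week 24 is not assured. Protocol 8.2.1 applies if the patient agrees to visits, 8.1 requires withdrawal for several safety criteria, and 8.2.2 covers patients who end participation. This stands: the full-retention figures are the upper end on retention.

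**Discontinuation.** Protocol 8.2 expects withdrawal to be uncommon, and 4.4.1 allows dose reduction or a hold of up to 7 days. At 10% to 15% against 5% stopping the ratio is only 1.02 to 1.03. This stands too.

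**Precision.** At 12% risk, 30 patients give 3.6 events per arm, so SE(log HR) is about √(1/3.6 + 1/3.6) = 0.75. A ratio of 1.10 is ln(1.10)/0.75 = 0.13 SE. The bias is small beside the noise, but it is systematic and avoidable.

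**Conclusion.** The point holds on the SAP as written: the adjudicated analysis uses different windows for events and for event-free follow-up. The upward bias in KM and hazard estimates is modest. At an assumed 12% risk with full retention, the spurious ratio is about 1.02 to 1.03 for 10% to 15% against 5% stopping, and 1.07 to 1.10 for 25% to 35% against 5%. It roughly halves with half the stoppers lost and is nil with all lost.

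A reader might infer more than the documents support:

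- *That the result is tilted against the active or higher-dose arm.* Protocol 4.7 reports dose-dependent gastrointestinal events in healthy subjects, but no discontinuation rates by arm are given. The bias falls on whichever arm has more or earlier stopping.
- *That event counts are inflated.* The crude number and percentage with an event are unaffected.
- *That no off-drug time counts without an event.* Stoppers still in contact contribute up to 30 days after last dose.
- *That the trial's conclusion or its type 1 error is at risk.* TTCW is an additional endpoint outside the Hochberg procedure (SAP 7.1.6), and two-sided log-rank error stays near 5%.

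**What to change.** Rewrite the censoring sentence in SAP 7.4.2 so that one window governs events and follow-up:

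- Main adjudicated analysis: count all first adjudicated CWEs to Week 24. Censor event-free subjects at the earliest of Week 24, first OLE dose and last main-study contact.
- Investigator-assessed sensitivity analysis: apply the same rule. Its present text names last contact only, with no Week 24 or OLE-dose limit, so it cannot simply be copied across. The two analyses would then differ only in assessor.
- If an on-treatment analysis is wanted, add it as a labelled sensitivity analysis in which both events and follow-up stop at last dose + 30 days.

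The first rule fits the ITT analysis and the protocol's continued follow-up after stopping drug. The cost is a few sentences and a small programming change, with no new data.

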7.4.3. Change from Baseline in ECHO Parameters

[figure not shown]
The following ECHO parameters will be summarized: Right Atrium area (cm^2), Tricuspid annular plane systole excursion [TAPSE] (cm), Tricuspid annular peak systolic myocardial velocity (m/sec), Right ventricular fractional area change [RVFAC] (%), Right ventricular end diastolic area [RVEDA] (cm^2), Right ventricular end systolic area [RVESA] (cm^2), Right Ventricular Pulmonary Artery contractile-pressure coupling (RV-PA coupling = TAPSE/SPAP [from RHC]), Right Ventricle free-wall thickness, Peak Tricuspid regurgitation velocity (m/sec), and Pericardial effusion (cm). The RHC and ECHO should be from the same visit, not necessarily the same date.

The change from baseline will be analyzed using the same ANCOVA model as specified in [Section 7.2](#).

[figure not shown]
7.4.4. Change from Baseline in PAH-SYMPACT

The PAH SYMPACT Questionnaire is an instrument for quantifying PAH symptoms and impacts. It is a brief, disease specific subject reported outcome (PRO) instrument possessing good psychometric properties.

PAH Symptoms Questionnaire is collected for 7 days at each scheduled visit.

PAH Impacts questionnaire are collected once each visit (on the day of the visit):

Scores for the individual items and domains ranged from 0 to 4, with higher scores indicating greater symptom severity or worse impact. Symptoms Domains include Cardiopulmonary Symptoms and Cardiovascular Symptoms. Impacts Domains include Physical Impacts and Cognitive/Emotional Impacts. The domain score derivations are as follows:

Symptoms Domain Score Derivation:

Mean weekly symptom item scores are calculated as an average of the daily item scores. At least 4 days must be available within 14 days prior to the visit to calculate an average. Day 7 must also be available to calculate the average. The days closest to the visit with non-missing data will be used for analyses.

Symptom domain score is then calculated as the average of the mean weekly scores for its included items.

Impacts Domain Score Derivation

Impact domain score is calculated as the average of the mean impact item scores for its included items.

Analysis

In cases where the tablets were not working, the data was recorded on paper and transcribed into the EDC. The primary analysis will use all available data (paper and tablet together). Paper ePROs were data entered in Unscheduled Visits in the EDC. Sensitivity analyses may be conducted using only tablet data.

PAH-SYMPACT domain scores will be analyzed using observed data and the same REML based MMRM model as specified in [Section 7.3.3](#).

Sensitivity analyses will be conducted using the single score at the scheduled visit (Day 7) instead of the mean weekly scores.

7.4.5. Change from Baseline REVEAL Lite 2 Score

REVEAL Lite 2 includes 6 non-invasive variables: FC, vital signs (SBP and HR), 6MWD, NT-proBNP, and renal insufficiency (by eGFR). Individual component scores are defined as follows:

1. New York Heart Association (NYHA) or WHO functional class (FC):

FC Class	REVEAL2 FC Component Score
I	-1
II	0
III	+1
IV	+2

2. Systolic BP:

Systolic BP (mmHg)	BP Component Score
< 110	+1
≥ 110	0

3. Heart Rate

Heart Rate (bpm)	Heart Rate Component Score
> 96	+1
≤ 96	0

4. 6-min walk distance (6MWD);

6MWD (meters)	6MWD Component Score
> 440	-2
320 - 440	-1
165 – <320	0
<165	+1

5. N-terminal prohormone of brain natriuretic peptide (NT-proBNP);

NT-proBNP	REVEAL2 FC Component Score
<35.4 pmol/L <300 pg/mL	-2
≥35.4 and <129.8 pmol/L ≥300 and <1100 pg/mL	0
≥129.8 pmol/L ≥ 1100 pg/mL	+2

6. Renal insufficiency:

eGFR (mL/min/1.73 m ²)	Renal Component Score
< 60 or reported AE of Renal Insufficiency	+1
≥ 60	0

REVEAL Lite 2 Score= Sum of 6 component scores + 6 (with scores ranging from 1 to 14).

For subjects with missing component score(s) for #2 (SBP), #3 (HR), or #6 (eGFR), the REVEAL Lite 2 score will still be calculated as the sum of the 3 remaining component scores. Otherwise, if any other components are missing, the REVEAL Lite 2 score will be set as missing.

The REVEAL Lite 2 score will be analyzed using observed data and the same REML based MMRM model as specified in [Section 7.3.3](#).

7.4.6. Time to Clinical Improvement (TTCI)

Subjects are considered as having clinical improvement on-treatment during the 24 weeks of the main study if they meet the following criteria:

- 10% increase in 6MWD or 30 meters increase AND
- improvement to WHO FC II or I, or maintenance of WHO FC II
- absence of a deterioration in clinical condition or death (defined as without an adjudicated clinical worsening event during the 24 weeks [see [Section 7.4.2](#)])

On-treatment is defined as randomization date through last dose of study drug + 30 days. TTCI is the number of days from the randomization date to the minimum of (date of the first assessment of 6MWD increase of 10% or 30 meters, first date improved WHO FC, last post-baseline date WHO FC II was maintained from baseline, censor date from an adjudicated TTCW). Subjects who do not improve during the 24 weeks of the main study will be censored at the first OLE dose date if enrolled into OLE or if not enrolled into OLE, the minimum of last dose of study drug + 30 days or date of last contact in the main study.

TTCI will be summarized using the same methods as specified above in [Section 7.4.2](#).

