9.1.2. Time to Clinical Improvement

TTCI will be evaluated by a multicomponent improvement score including WHO FC and 6MWT measurements: a > 10% increase in 6MWD or 30 meters AND an improvement to or maintenance of WHO FC II symptomatology, in the absence of a deterioration in clinical condition or death during the 24 weeks of the Main Study.

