4.7. Visits

4.7.1. Windows

Each visit will be denoted by its visit “Week”. The first dose day is denoted as Day 1. In data listings, the relative study day of all dates from first dose will be presented.

Unless otherwise specified, scheduled assessments will be used for tabulated summaries. In the event of unscheduled visits, follow-up, or early treatment termination (ET) assessments, these will be reassigned to a scheduled visit for analysis purposes according to [Table 4](#) (RHC), [Table 5](#) (6MWT, WHO-FC, and NT-proBNP), [Table 6](#) (Clinical Laboratory Evaluations, Vital Signs, ECGs), and [Table 7](#) (Echocardiography and PAH-SYMPACT) for on treatment assessments. If multiple assessments occur within a single visit window, after reassignment of unscheduled visits and ET assessments, the assessment closest to the target day of the visit window will be used in the analysis. If there is a tie, the later assessment will be used in the analysis.

Table 4: Treatment Period Visit Windows: RHC

Target Scheduled Visit	Target Study Day ^a	Analysis Window Study Day ^a	
		Low	High
Baseline ^b	1	See Section 4.7.2	
Week 24	169	2	197 ^c

^a Study day will be calculated from first dose of study drug.

^b Baseline is defined in [Section 4.7.2](#).

^c Must be prior to first dose in the OLE.

Table 5: Treatment Period Visit Windows: 6MWT, WHO-FC, NT-proBNP

Target Scheduled Visit	Target Study Day ^a	Analysis Window Study Day ^a	
		Low	High
Baseline ^b	1	See Section 4.7.2	
Week 4	29	2	42
Week 12	85	43	126
Week 24	169	127	182 ^c

^a Study day will be calculated from first dose of study drug.

^b Baseline is defined in [Section 4.7.2](#).

^c Must be prior to first dose in the OLE.

Table 6: Treatment Period Visit Windows: Clinical Laboratory Evaluations, Vital Signs, and ECGs

Target Scheduled Visit	Target Study Day ^a	Analysis Window Study Day ^a	
		Low	High
Baseline ^b	1	See Section 4.7.2	
Week 4	29	2	42
Week 8	57	43	71
Week 12	85	72	105
Week 18	127	106	147
Week 24	169	148	182 ^c

^a Study day will be calculated from first dose of study drug.

^b Baseline is defined in [Section 4.7.2](#).

^c Must be prior to first dose in the OLE.

Table 7: Treatment Period Visit Windows: Echocardiography and PAH-SYMPACT

Target Scheduled Visit	Target Study Day ^a	Analysis Window Study Day ^a	
		Low	High
Baseline ^b	1	See Section 4.7.2	
Week 12	85	2	126
Week 24	169	127	182 ^c

^a Study day will be calculated from first dose of study drug.

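### TTCI dates a two-criterion response at the earlier criterion, and the REVEAL Lite 2 rule for missing items can discard observed components

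*SAP*

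**What the plan says.** **TTCI.** SAP 7.4.6 joins the two criteria: "10% increase in 6MWD or 30 meters increase AND" an FC criterion (improvement to class II or I, or class II maintained), with no adjudicated clinical worsening event. Protocol 9.1.2 uses the same conjunction: "10% increase in 6MWD or 30 meters AND an improvement to or maintenance of WHO FC II symptomatology". The SAP then defines the time: "TTCI is the number of days from the randomization date to the minimum of (date of the first assessment of 6MWD increase of 10" percent or 30 m, and three further dates). Those are the first date of improved FC, the "last post-baseline date WHO FC II was maintained from baseline", and the "censor date from an adjudicated TTCW". On-treatment runs from randomization to last dose plus 30 days. The analysis methods are those of SAP 7.4.2: Kaplan-Meier, stratified log-rank and Cox.

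**REVEAL Lite 2.** SAP 7.4.5 defines the score as the sum of six components plus 6, with a range of 1 to 14. If a component score for SBP, HR or eGFR is missing, "the REVEAL Lite 2 score will still be calculated as the sum of the 3 remaining component scores". If FC, 6MWD or NT-proBNP is missing, the score is missing.

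**The concern.** A response that needs two conditions does not exist until the second is met. A minimum over the component dates can place the event at a visit where only one has been met. Who counts as an improver does not change, but the event times entering the survival analyses do.

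Three groups are exposed:
- patients in FC III at baseline;
- patients in FC II at baseline who reach FC I before meeting the walk criterion;
- patients in FC II at baseline whose last FC II date precedes the walk criterion, because FC later worsens or is missing.

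For REVEAL Lite 2, the trigger is one or more missing items, but the count of three remaining components is right only when all three are missing. With one or two missing, observed items are thrown away. The constant of 6 is also not restated, so two programmers could derive different scores.

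**Working it through.** **TTCI inputs.** SAP 4.7.1, Table 5 ("Treatment Period Visit Windows: 6MWT, WHO-FC, NT-proBNP"), gives post-baseline target Days 29, 85 and 169. Visits are taken to fall on target.

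**TTCI, FC III at baseline.** Each criterion is met at one or more of three visits, which gives 7 patterns per criterion and 7 x 7 = 49 in all. A criterion is first met at visit 1, 2 or 3 in 4, 2 or 1 of its 7 patterns. Compare the minimum with the later of the two first dates:

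| First visits | Patterns | Dated early by |
|---|---|---|
| Same visit | 16 + 4 + 1 = 21 | 0 |
| 1 and 2 | 2 x 4 x 2 = 16 | 85 - 29 = 56 days |
| 2 and 3 | 2 x 2 x 1 = 4 | 169 - 85 = 84 days |
| 1 and 3 | 2 x 4 x 1 = 8 | 169 - 29 = 140 days |

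So 28 of 49 are dated early. Example: FC III at baseline, 30 m gained from Day 29, FC II first reached at Day 169. The SAP gives Day 29, but both criteria have been met only by Day 169.

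**TTCI, FC II at baseline.**
- FC II at every visit: the last FC II date is Day 169, so the minimum is the walk date. All 7 walk patterns are dated correctly.
- FC I from Day 29, walk first met at Day 169: dated Day 29, 140 days early.
- FC II at Day 29, FC III at Days 85 and 169, walk first met at Day 169: dated Day 29, if this patient counts as an improver. The SAP does not say when class II must be maintained.

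**Swapping minimum for maximum is not enough.** With the last FC II date kept, a patient in FC II throughout would always be dated Day 169. Of the 7 walk patterns, 4 would be 140 days late, 2 would be 84 days late and 1 would be correct.

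**TTCW censor date.** SAP 7.4.2 sets it for "Subjects who do not have an adjudicated CWE during the 24 weeks of the main study": first OLE dose, or otherwise the earlier of last dose plus 30 days and last contact. An improver has no adjudicated event. If component dates are held to the on-treatment window, and before the first OLE dose as Table 5 requires, the censor date cannot precede them, so the term adds nothing.

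**REVEAL Lite 2, the plan's own range.** The components are FC -1 to 2, SBP 0 or 1, HR 0 or 1, 6MWD -2 to 1, NT-proBNP -2, 0 or 2, and renal 0 or 1. Minimum: -1 - 2 - 2 + 6 = 1. Maximum: 2 + 1 + 1 + 1 + 2 + 1 + 6 = 14. The stated 1 to 14 reproduces.

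**REVEAL Lite 2, missing patterns.** Three patterns have one item missing (5 components remain), three have two missing (4 remain) and one has all three missing (3 remain). A count of three is right in 1 of 7.

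**REVEAL Lite 2, one item missing, constant kept.** FC, 6MWD and NT-proBNP give 4 x 4 x 3 = 48 combinations. Times 4 states of the two observed items, that is 192. The dropped items sum to 0, 1 or 2 in 48, 96 and 48 of them, so 96 + 48 = 144 lose observed points. Restricted to FC II or III, 15 of 96 move from 6 or above to below 6.

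Example: FC II (0), 6MWD 350 m (-1), NT-proBNP 500 pg/mL (0), SBP 105 (+1), eGFR 55 (+1), HR missing. Three components plus 6 give 5. All observed components plus 6 give 7. The complete-data score would be 7 or 8.

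**The case against.** **The benchmark.** The documents do not say which visit is the correct event date, and the later of two first dates does not guarantee that both criteria hold on that date. This stands. In 14 of the 28 early patterns the later date falls on a visit where only one criterion holds, and in 12 of the 49 the two never hold together. The later date ensures only that both criteria have been met by then. A same-visit requirement would change who is an improver.

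**The constant.** A reader might infer that scores with a gap run from -5 to +5, with 28 of 48 combinations below 1, off the scale of Protocol Appendix 13. That needs the constant to be dropped. The formula with the constant stands just above the missing-item rule in the same section, so it was probably intended. The wording should be repaired, but the harm should not be sized on that reading.

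**The baseline subgroup.** A reader might also infer that patients would be misplaced in the SAP 7.1.7 split at a score of 6. It is possible but unlikely. SAP 4.7.2 takes the last evaluation before randomization, so a Screening value can fill a Day 1 gap. Vital signs and laboratory tests are scheduled at both visits (Protocol 1.3), and Screening blood pressure and eGFR are needed for eligibility (Protocol 5.2).

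**Bias between arms.** Nothing in the documents shows that early dating would favour one arm, and none is claimed.

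**Importance.** TTCI is exploratory, REVEAL Lite 2 is additional, and formal multiplicity control covers only the primary endpoint. That limits the weight of the point but does not make either rule right.

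**Conclusion.** Both rules need correction. The TTCI rule dates improvers too early whenever they first meet the two criteria at different visits: by 56, 84 or 140 days on target days, in 28 of 49 patterns for FC III patients. Some FC II patients are affected too; those in FC II at every visit are not. The REVEAL Lite 2 rule is wrong for one or two missing items. With one missing and the constant kept, it loses 1 or 2 observed points in 144 of 192 combinations.

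The counts weight every pattern or score combination equally and are not patient frequencies, which the documents do not give. REVEAL Lite 2 gaps should be uncommon, given the visit schedule and the use of local laboratory results (SAP 8.3). The set of TTCI improvers and the primary PVR analysis are unaffected.

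**What to change.** **TTCI (SAP 7.4.6).** Leave the responder definition as it is. Date the event at the later of:
- (a) the first on-treatment date the 6MWD criterion is met;
- (b) the first on-treatment post-baseline date the FC criterion is met (improved to class II or I, or still in class II).

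Use the first FC II-maintained date, not the last. Restate the on-treatment window here and remove the TTCW censor date from the event-date formula. Record separately whether the sponsor wants both criteria to hold at the same visit.

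**REVEAL Lite 2 (SAP 7.4.5).** Sum all available component scores, count a missing SBP, HR or renal component score as 0, and add 6. Keep the renal component at +1 when renal insufficiency is reported, even without an eGFR, as SAP 7.4.5 and Protocol Appendix 13 provide. Keep the score missing if FC, 6MWD or NT-proBNP is missing. State that a missing item is assumed normal, with an error of at most 1 point per item.

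**Cost.** A few SAP sentences and the matching derivation code, with no new data. SAP Section 1 allows changes to planned analyses without an updated SAP, with significant ones reported in the CSR.
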